#### 9.5.2.4 Duration of ICU stay

The duration of ICU stay will be derived as described in Section 5. This duration is equivalent to time to ICU discharge. The duration of ICU stay will be analyzed as described for time to freedom from mechanical ventilation.

#### 9.5.2.5 Mortality

Frequency counts and percentages for the number of patients who die while in ICU and also the number and percentage of patients who die within the first 30 days post-transplant (derived as latest date of reperfusion + 30) will be presented by treatment group. This table will be presented for the ITT population only.

#### 9.5.2.6 Pulmonary Function Tests

Summary statistics for FEV1 and FVC measured at Month 1 will be presented for the ITT population by treatment group and also for each treatment group and transplant type combinations.

#### 9.5.2.7 Acute Rejection Episodes

The number and percentage of patients reporting at least one acute rejection episode up to and including Month 1 will be reported by treatment group and also by treatment group and transplant type. The total number of episodes will also be reported for each treatment group and each treatment group and transplant type combination. This summary will be presented for the ITT population only.

### 9.6 Safety analyses

#### 9.6.1 Extent of Study Drug Exposure

Summary statistics for duration of study drug infusion and amount of study drug infused (see Section 5 for definition) will be presented by treatment group.

#### 9.6.2 Adverse events

A summary of treatment-emergent adverse events (see Section 5 for definition) reported between start of infusion and the Month 1 visit, including the total number of events reported, the number and percentage of patients reporting at least one adverse event, the number and percentage of patients withdrawing prematurely due to an adverse event, the number and percentage of patients with at least one serious adverse event and the number and percentage of deaths, will be presented by treatment. In addition, a summary of the event by each category of drug relationship will be presented for adverse events and also for serious adverse events.

A breakdown of the number and percentage of patients reporting each adverse event, categorized by body system and preferred term coded according to the MedDRA dictionary, will be presented. Note that counting will be of patients not events and patients are only counted once within each preferred term.

A further tabulation of these data, broken down by relationship to study drug, will be presented. Patients with multiple events within a particular body system or preferred term will be counted under the category of their most drug-related event within that body system or preferred term.

Relationship to study drug is categorized as none, unlikely, possible, probable and highly probable as recorded on the CRF. Each category of relationship will be presented on a separate page.

A summary of events reported, broken down by severity (mild, moderate, severe, life threatening), will also be provided. Patients with multiple events within a particular body system or preferred term will be counted under the category of their most severe event within that body system or preferred term. Each category of severity will be presented on a separate page.

A summary of adverse events leading to premature withdrawal will be provided, grouped by body system and preferred term.

All adverse events recorded on the CRF will be listed.

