6.3.2. Criteria for discontinuation of Investigational Product

Administration of the Investigational Product should be immediately discontinued in case the patient develops renal or hepatic dysfunction defined as:

renal dysfunction: the occurrence of both CL_{cr} < 60 mL/min and urine output < 0.5 mL/kg/hour on two consecutive sampling time points (12, 24, 36 hours after the beginning of Investigational Product infusion).

hepatic dysfunction: bilirubin exceeding 3 mg/dL and/or transaminases >3X upper limit of normal).

Phase 1 studies in patients with ESRD have shown that renal function has a profound effect on plasma concentrations of a major, marginally active metabolite, carboxy-repertaxin (DF2243Y), which was found to accumulate over time along with the increased elimination half-life. Even if toxicological results to date suggest that DF2243Y does not raise any safety concern, limited experience in humans recommends to discontinue the drug in case of renal impairment as it would not be possible to predict the risk associated with elevated plasma levels. However, transient alterations of serum creatinine or urine output, as defined above, do not indicate a renal dysfunction that would cause impaired excretion of DF2243Y. Because repertaxin undergoes extensive hepatic metabolism, it is also recommended that the infusion is discontinued in case of hepatic dysfunction to avoid an increase of plasma level of repertaxin, exceeding the target and safe concentration.

CL_{cr}, urine output, bilirubin and transaminases will be evaluated at 12, 24 and 36 hours after the beginning of Investigational Product infusion. Samples will be processed immediately and results made available as soon as possible to the Investigator. Urine output will be calculated for each of the 12 hour periods: from start of infusion to 12 hours, 12-24 hours, and 24-36 hours.

Investigational Product will also be immediately discontinued in the event of any other possibly drug related occurrences that the Investigator believes might compromise patient safety.

If the Investigational Product therapy is prematurely discontinued the primary reason for discontinuation must be recorded in the CRF. Patients who discontinue the treatment with the Investigational Product will not be withdrawn from the study by default, but will complete observations as per the protocol, unless otherwise withdrawn at the Investigator's decision.

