### 9.2 Patient Disposition

The number and percentage of patients screened, randomized and treated in the study will be presented, together with the number and percentage of patients who withdrew from the study prematurely prior to Month 1 and a breakdown of the corresponding reasons for withdrawal. The number and percentage of patients included in each of the ITT, PP and safety analysis populations will also be included. Screening data recorded for patients who do not proceed to transplant with study drug administration will be listed separately in the report. The exact format of the listings will be discussed with Dompé when the total number of patients randomized but not treated/transplanted is known.

A tabulation of the number and percentage of patients randomized at each center will be presented.

All data relating to study completion or withdrawal and inclusion in the analysis populations will also be listed.

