**Listings**

2.1.1	Patient Disposition (All Randomized Patients)
2.1.2	Protocol Deviations (All Randomized Patients)
2.1.3	Month 1 Completion and Reasons for Premature Withdrawal from Study (All Randomized Patients)
2.1.4	Reasons Screened but not Randomized (All Screened Patients)
2.2	Demographic Data
2.5.1	Study Treatment Administration – Dates and Times
2.5.2	Study Treatment Administration – Termination of Infusion
2.6.1	Individual Efficacy Response Data – PaO 2 /FiO 2 ratio
2.6.2	Individual Efficacy Response Data – PGD Score
2.6.3	Individual Efficacy Response Data – Time to Freedom from Mechanical Ventilation
2.6.4	Individual Efficacy Response Data – Duration of Hospital Stay
2.6.5	Vital Status
2.6.6	Pulmonary Function Tests
2.7.1	Adverse Events Reported up to Month 1
2.7.2	Serious Adverse Events Reported up to Month 1
2.8.1	Laboratory Data: Hematology - Patient Profiles
2.8.2	Laboratory Data: Clinical Chemistry - Patient Profiles
2.8.3	Laboratory Data: Coagulation - Patient Profiles

4.1	Visit Dates
4.2.1	Inclusion Criteria
4.2.2	Exclusion Criteria
4.3.1	Recipient Information – Transplant type
4.3.2	Recipient Information – CMV Status and Extrapulmonary site of infection
4.4	Significant Medical History
4.5.1	Donor Information – Demography and Cause of Death
4.5.2	Donor Information – Lung Flush Solutions
4.6.1	Transplant Information – Dates and Times
4.6.2	Transplant Information – Procedures and Complications
4.7	Preparation of Infusion Bags
4.8	ICU Admission
4.9	Bronchoalveolar Lavage
4.10	ICU Discharge and Mechanical Ventilation Weaning Tracking
4.11.1	Clinical Diagnosis of PGD
4.11.2	PaO 2 /FiO 2 Ratio for Patients Diagnosed with PGD
4.11.3	PGD Score for Patients Diagnosed with PGD
4.11.4	Bronchoalveolar Lavage or Biopsy Patients Diagnosed with PGD
4.12	First Extubation and ICU Discharge
4.13	ICU Readmission and Hospital Discharge
4.14	Patient Status at Month 1
4.15	Death Report
4.15.1	Laboratory Data: Hematology – Variable Profiles
4.15.2	Laboratory Data: Clinical Chemistry – Variable Profiles
4.15.3	Laboratory Data: Coagulation – Variable Profiles
4.15.4	Creatinine Clearance
4.15.5	Renal and Hepatic Function
4.16	Prior and Concomitant Medications Reported up to Month 1
4.17.1	Vital Signs and Cardiopulmonary Measurements
4.17.2	Cardiopulmonary Measurements for Patients Diagnosed with PGD
4.18	Pharmacokinetic Sample Collection
4.19	Investigator's Declaration
4.20	Investigator Comments

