## Examples of adverse event presentations

Table 3.2.1.1 Summary of Treatment-Emergent Adverse Events (TEAEs)

	Treatment	
	Repertaxin	Placebo
Total number of TEAEs	XX	XX
Number of Patients with:		
At least one TEAE	XX (XX%)	XX (XX%)
Withdrawing prematurely due to TEAE	XX (XX%)	XX (XX%)
At least one Serious TEAE	XX (XX%)	XX (XX%)
TEAE leading to death	XX (XX%)	XX (XX%)
TEAEs - Most Serious Relationship to Study Drug		
Unrelated	XX (XX%)	XX (XX%)
Unlikely	XX (XX%)	XX (XX%)
Possible	XX (XX%)	XX (XX%)
Probable	XX (XX%)	XX (XX%)
Highly Probable	XX (XX%)	XX (XX%)
Serious TEAEs - Most Serious Relationship to Study Drug		
Unrelated	XX (XX%)	XX (XX%)
Unlikely	XX (XX%)	XX (XX%)
Possible	XX (XX%)	XX (XX%)
Probable	XX (XX%)	XX (XX%)
Highly Probable	XX (XX%)	XX (XX%)

Table 9.2.1.2 Treatment-Emergent Adverse Events by Body System and Preferred Term

MedDRA Body System & Preferred Term	Treatment	
	Repertaxin	Placebo
PAIN	XX (XX%)	XX (XX%)
Pain- other	XX (XX%)	XX (XX%)
Bone Pain	XX (XX%)	XX (XX%)
Abdominal	XX (XX%)	XX (XX%)
Headache	XX (XX%)	XX (XX%)
Chest pain	XX (XX%)	XX (XX%)
GASTROINTESTINAL	XX (XX%)	XX (XX%)
Constipation	XX (XX%)	XX (XX%)
Nausea	XX (XX%)	XX (XX%)
Anorexia	XX (XX%)	XX (XX%)
Vomiting	XX (XX%)	XX (XX%)
Diarrhea	XX (XX%)	XX (XX%)

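### The SAP's adverse event tables count premature withdrawal, apparently from the study, so infusions stopped early for safety are not tabulated by arm and reason

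*SAP*

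**What the plan says.** **Protocol 6.3.2.** The infusion is to be stopped at once for renal dysfunction, hepatic dysfunction, or another possibly drug-related occurrence that the investigator thinks could compromise safety. Stopping the drug is kept apart from leaving the study: "Patients who discontinue the treatment with the Investigational Product will not be withdrawn from the study by default". They complete the planned observations unless the investigator decides to withdraw them. When the infusion ends early, "the primary reason for discontinuation must be recorded in the CRF".

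**SAP safety tables.** SAP 9.6.2 plans a summary that includes "the number and percentage of patients withdrawing prematurely due to an adverse event", and then: "A summary of adverse events leading to premature withdrawal will be provided, grouped by body system and preferred term." SAP 9.6.3 plans the same for SAEs. The outputs are Tables 3.2.1.1, 3.2.1.5 and 3.2.2.4. The row in the shell for Table 3.2.1.1 reads "Withdrawing prematurely due to TEAE".

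**What the term means elsewhere in the SAP.** SAP 9.2 reports "the number and percentage of patients who withdrew from the study prematurely prior to Month 1", and the title of Listing 2.1.3 includes "Reasons for Premature Withdrawal from Study".

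**Other outputs that touch early stopping.**
- Table 3.1, described in SAP 9.6.1: "Summary statistics for duration of study drug infusion and amount of study drug infused", by treatment group.
- Table 1.3 (SAP 9.3 with 6.2): deviations that exclude patients from the ITT or PP population, by treatment group. An infusion shorter than 24 h is one of them.
- Listing 2.5.2: termination of infusion, by patient.
- SAP 9.6.4 and Listings 4.15.4 and 4.15.5: the on-infusion creatinine clearance and the renal and hepatic function results, listed only.

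**The concern.** Safety is a stated objective. Protocol 6.3.2 explains why the drug is stopped: a metabolite accumulates when renal function is poor, parent drug levels may rise when hepatic function is poor, and human experience is limited. How often a 48 h infusion had to be stopped for these reasons in each arm is therefore a direct tolerability result.

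If premature withdrawal means leaving the study, the tables that seem to answer this question answer a different one. A patient whose infusion is stopped for renal dysfunction, and who then completes follow-up as the protocol directs, does not count in Tables 3.2.1.1, 3.2.1.5 or 3.2.2.4 as withdrawing because of the event. The reason for stopping is collected but reaches no planned table.

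**Working it through.** The plan states no figure on this point, so there is none to reproduce. The check has two parts.

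**1. Where a safety stop would appear, taking premature withdrawal as leaving the study**

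| Output | By arm? | Counts infusion stops? | Gives the reason? |
|---|---|---|---|
| Tables 3.2.1.1, 3.2.1.5, 3.2.2.4 | Yes | Only if the patient also leaves the study | Yes, for those patients |
| Table 3.1 | Yes | No; duration and volume only | No |
| Table 1.3 | Yes | Only infusions under 24 h | No |
| Listing 2.5.2 | Patient level | Yes, by reading the listing | Not specified in the SAP |

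*Timing against the 24 h cut in Table 1.3.* Protocol 6.3.2 samples at 12, 24 and 36 h after the start of infusion. The renal criterion needs two consecutive time points, so it is nominally first met at 24 h. With the ±4 h window in Protocol Appendix 6, the second sample can fall at 24 − 4 = 20 h. The hepatic criterion carries no two-sample requirement, so it can be met at 12 h. Table 1.3 would thus catch early hepatic stops and a few renal ones, mixed with stops for any other reason, and would miss every stop from 24 h up to 48 h.

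**2. What the exposure summaries would show**

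Inputs: 50 patients per arm (SAP 3.2) and a planned infusion of 48 h. The number and time of stops are assumptions, because the documents give no stopping rate. If k of 50 infusions stop at h hours and the rest run to 48 h:

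mean duration = 48 − (k/50) × (48 − h)

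- 6 v 1 stops at 24 h: 48 − 0.12 × 24 = 45.12 h; 48 − 0.02 × 24 = 47.52 h.
- 8 v 2 stops at 24 h: 48 − 0.16 × 24 = 44.16 h; 48 − 0.04 × 24 = 47.04 h.
- 5 v 1 stops at 36 h: 48 − 0.10 × 12 = 46.80 h; 48 − 0.02 × 12 = 47.76 h.

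| Assumed stops, repertaxin v placebo | Rate | Mean duration (h) | Median (h) | Infusions under 24 h |
|---|---|---|---|---|
| 6 v 1 at 24 h | 12% v 2% | 45.1 v 47.5 | 48 v 48 | 0 v 0 |
| 8 v 2 at 24 h | 16% v 4% | 44.2 v 47.0 | 48 v 48 | 0 v 0 |
| 5 v 1 at 36 h | 10% v 2% | 46.8 v 47.8 | 48 v 48 | 0 v 0 |

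For 6 v 1 at 24 h, the SD is 24 × √[p(1 − p) × 50/49]. With p = 0.12 it is 7.9 h, and with p = 0.02 it is 3.4 h. The minimum is 24 h in both arms.

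In the same 6 v 1 case, the withdrawal tables would show anything from 0 v 0, if all seven patients stay in the study, to 6 v 1, if the investigator withdraws all seven. Under the default in Protocol 6.3.2 the result would lie towards the lower end.

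**The case against.** Four points on the other side have weight.

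- **The reading of the term is inferred.** SAP 9.6.2, SAP 9.6.3 and the table titles never add that the withdrawal is from the study. The sponsor may have meant withdrawal of treatment. This stands: the term is undefined there, and the study reading comes from SAP 9.2 and Listing 2.1.3. The wording needs settling on either reading.
- **Early stopping is not invisible.** In the 6 v 1 example, Table 3.1 would show a lower mean, a larger SD and a 24 h minimum. Table 1.3 would count hepatic stops at 12 h. In about 100 patients, Listing 2.5.2 can be counted by hand. This also stands, but none of it is a planned by-arm count with reasons.
- **The events themselves are still reported.** A renal or hepatic event recorded as an AE appears by arm in the incidence, relationship and severity tables. What is lost is its link to stopping the drug.
- **No protocol commitment is broken.** Protocol 9.4.6 promises incidence, severity and relationship, and no table of events leading to discontinuation. That is correct, and it limits the weight of the point.

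A reader might infer that the report would look as if no infusion had been stopped for safety. The documents do not support that. Duration, volume, infusions under 24 h and the termination listing are all reported, and Protocol 6.3.2 and 7.10.1 let the investigator withdraw a patient, who would then enter the withdrawal tables. A 0 v 0 result is an assumed worst case, not a prediction.

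**Conclusion.** The point holds as a gap in safety reporting. On the more natural reading of premature withdrawal, the AE and SAE withdrawal tables could miss most infusions stopped for safety, and no other planned table gives those stops by arm and reason. Tables 3.1 and 1.3 give a partial signal only.

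The size cannot be fixed from the documents. The illustration shows only that differences such as 12% v 2% or 16% v 4% could leave both medians at 48 h and the under-24 h count at 0 v 0, with means about 2 to 3 h apart. It assumes 50 patients per arm, every other infusion running the full 48 h, and all stops at exactly 24 h.

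No efficacy estimate or test is affected, and the stopping criteria themselves are not questioned. This is a cheap improvement.

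**What to change.** 1. In SAP 9.6.2, SAP 9.6.3 and Tables 3.2.1.1, 3.2.1.5 and 3.2.2.4, add events leading to premature discontinuation of study drug infusion. Keep study withdrawal as a separate row or table, and say explicitly that it means leaving the study.
2. In Table 3.1, add by arm the number and percentage of patients whose infusion was stopped prematurely, by primary reason on the CRF and by time of stopping. The natural reason groups are renal criterion, hepatic criterion, other AE and other. They must be matched to the CRF fields, which are not among the documents.

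The cost is a few sentences and table rows. Protocol 6.3.2 already requires the reason, and Protocol 6.4.1 already has infusion start and end times recorded, so no new data are needed. SAP 1.1 says the plan will be finalised before database lock, so the change can be made while the study is still blinded.

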### 9.6.3 Serious Adverse Events

A breakdown of the number and percentage of patients reporting each serious adverse event (SAE) between the start of infusion and the Month 1 visit, categorized by body system and preferred term coded according to the MedDRA dictionary, will be presented.

A further tabulation of these data, broken down by relationship to study drug, will be presented. Patients with multiple SAEs within a particular body system or preferred term will be counted under the category of their most drug-related SAE within that body system or preferred term. Relationship to study drug is categorized as none, unlikely, possible, probable and highly probable as recorded on the CRF. Each category of relationship will be presented on a separate page.

A summary of SAEs reported, broken down by severity (mild, moderate, severe, life threatening), will also be provided. Patients with multiple SAEs within a particular body system or preferred term will be counted under the category of their most severe SAE within that body system or preferred term. Each category of severity will be presented on a separate page.

A summary of SAEs leading to premature withdrawal will be provided, grouped by body system and preferred term.

### 9.6.4 Laboratory data

Samples for safety laboratory tests for hematology, clinical chemistry and coagulation are taken at Screening and hospital discharge. The following parameters will be included in the summary data presentations:

Hematology: hematocrit, hemoglobin, red blood cells, white blood cells, neutrophils, lymphocytes, monocytes, eosinophils, basophils

Clinical chemistry: sodium, potassium, chloride, bicarbonate, blood urea nitrogen (BUN), total bilirubin, alanine aminotransferase (ALT), aspartate aminotransferase (AST), serum creatinine

Coagulation: activated partial thromboplastin time (APTT), prothrombin time (PT), INR

Note: patients will either have a value for PT or INR at each time point.

Results for each parameter at screening and hospital discharge will be assessed as being below the lower limit of the normal range, within the normal range or above the upper limit of the normal range. The number and percentage of patients with out-of-range results and the number and percentage of patients with clinically significant out-of-range results will be presented for each parameter at each time point, together with the number of patients with results for that parameter and time point. Shifts in laboratory parameters during the hospital stay will also be presented for each parameter.

Creatinine clearance is calculated using Cockcroft-Gault formula at Screening and at 12, 24 and 36 hours post ICU admission for the assessment of renal and hepatic function during the study.

These data are used for assessment of patient during the study conduct phase and will be listed only.

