4.2.4. Safety endpoints

- AE recording.
- Standard laboratory tests including hematology (hematocrit, hemoglobin, red blood cells, platelets, white blood cells, differential white blood cells count), and clinical chemistry (sodium, chloride, potassium, bicarbonate, serum creatinine, blood urea nitrogen, total bilirubin, alanine aminotransferase (ALT), aspartate aminotransferase (AST), prothrombin time or international normalized ratio, partial thromboplastin time). Laboratory tests will be performed at screening and at hospital discharge.
- Vital signs, i.e. blood pressure (BP) and heart rate (HR), assessed at screening, on ICU admission, and then q12 hours up to ICU discharge or up to 5 days after ICU admission, whichever occurs earlier.
- Cardiopulmonary physiologic measurements, including cardiac output (CO), pulmonary artery pressure (PA pressure), systemic vascular resistance (SVR), pulmonary vascular resistance (PVR), pulmonary capillary wedge pressure (PCWP), right atrial pressure (CVP). Assessment will be performed on ICU admission, and then q12 hours when PA catheter is present, up to ICU discharge or up to 5 days after ICU admission, whichever occurs earlier. Additional cardiopulmonary data obtained as per center standard of care will be collected in patients with clinical diagnosis of PGD up to the clinical recovery of the condition.

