7.1. SCREENING AND RANDOMIZATION

Potential study patients will be identified whilst on the center transplant waiting list. On arrival at the center for transplantation, consented patients will undergo confirmatory screening for the study.

Compliance with inclusion/exclusion criteria will be verified vs demographic and clinical information available as per Organ Procurement Agency - e.g. United Network for Organ Sharing (UNOS) - form and standard clinical practice.

Laboratory tests (hematocrit, hemoglobin, red blood cells, platelets, white blood cells, differential white blood cells count, sodium, chloride, potassium, bicarbonate, serum creatinine, blood urea nitrogen, total bilirubin, ALT, AST, prothrombin time or international normalized ratio, partial thromboplastin time) will be performed by local laboratories.

Screening also includes measurement of BP, HR, body weight (kg), and testing for renal and hepatic function, as well as for extra-respiratory tract site of infection.

Renal function will be evaluated by CL_{Cr}, calculated according to the following formula (*Cockcroft-Gault; 1976*):

$$\text{Male: CL}_{Cr} = \frac{[140 - \text{age (years)}] \bullet \text{Weight (kg)}}{\text{Serum Creatinine (mmol / L)} \bullet 815}$$

$$\text{Female: CL}_{Cr} = \frac{[140 - \text{age (years)}] \bullet \text{Weight (kg)}}{\text{Serum Creatinine (mmol / L)} \bullet 815} \bullet 0.85$$

Hepatic function will be evaluated by bilirubin (mg/dL) and transaminases (ALT and AST).

Extra-respiratory tract sites of infection will be diagnosed by blood culture(s) and/or fever associated with other signs of systemic sepsis syndrome. Previous results of blood cultures can be used to verify inclusion criteria, provided that the sample has not been obtained earlier than 72 hours prior to randomization.

Eligible patients will be randomized (randomization number assigned) by an Investigator or designee before proceeding to the operating room. The Investigator will forward to the Pharmacy an order to start preparation of Investigational Product dosing solution.

A screening form will be completed for all patients who signed the Patient Informed Consent Document, regardless of sequent entry into the study. Patients will be identified by their

initials and date of birth; in addition their race, sex and reasons for exclusion from the study will be recorded.

If entered into the study, the following recipient data will be recorded in the CRF:

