9.4.6. Safety analysis

Safety variables will be presented for the Safety population.

AEs will be presented, by treatment group, in terms of the incidence, severity and relationship to the study drug, overall and by body system and preferred term. SAEs will be presented in the same way.

Laboratory tests are performed at screening and at hospital discharge and shift tables will be used to present shifts from within/outside the normal range between screening and discharge.

Vital signs at each time point, the change in vital signs from screening to each time point, and cardiopulmonary physiologic measurements at each time point will be presented using descriptive statistics.

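### Platelets are a protocol safety test due a screening-to-discharge shift table, but the SAP's list of summarised laboratory parameters leaves them out

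*SAP*

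**What the plan says.** Protocol 4.2.4 (Safety endpoints) gives the hematology tests as "hematocrit, hemoglobin, red blood cells, platelets, white blood cells, differential white blood cells count", and says of the whole laboratory panel: "Laboratory tests will be performed at screening and at hospital discharge". Protocol 7.1 names platelets again among the tests done by the local laboratories at screening. For the analysis, Protocol 9.4.6 says that "shift tables will be used to present shifts from within/outside the normal range between screening and discharge". It makes no exception for any test.

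SAP 9.6.4 introduces its list with "The following parameters will be included in the summary data presentations". The hematology line that follows is "Hematology: hematocrit, hemoglobin, red blood cells, white blood cells, neutrophils, lymphocytes, monocytes, eosinophils, basophils". The clinical chemistry and coagulation lines come next. For each parameter, the section then specifies counts of out-of-range and clinically significant out-of-range results at each time point, together with shifts over the hospital stay. The corresponding hematology outputs in SAP section 11 are Table 3.3.1.1 (clinically significant results) and Table 3.3.2.1 (shifts). SAP 1.2 records no changes from the protocol.

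**The concern.** The protocol promises a by-arm shift table for a named safety test, and the SAP's specification does not deliver it. The departure is neither declared nor explained. Safety is a stated objective of the trial, and about 100 patients are to be randomised, so a between-arm pattern in one blood count is much easier to see in a table than by reading individual values.

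The SAP's own quality control would not expose the gap. Section 10 requires each output to be checked against the plan's specifications, and a hematology table without platelets matches the list in 9.6.4.

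**Working it through.** No sample size, power or significance calculation bears on this point. The check is an item-by-item comparison of the laboratory panel in Protocol 4.2.4 with the summarised parameters in SAP 9.6.4.

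| Protocol 4.2.4 item | In the SAP 9.6.4 list? |
|---|---|
| Hematocrit | yes |
| Hemoglobin | yes |
| Red blood cells | yes |
| Platelets | **no** |
| White blood cells | yes |
| Differential white cell count | yes, expanded to five cell types |
| Sodium, chloride, potassium, bicarbonate | yes (4 items) |
| Serum creatinine, blood urea nitrogen | yes (2 items) |
| Total bilirubin, ALT, AST | yes (3 items) |
| Prothrombin time or INR | yes |
| Partial thromboplastin time | yes, as APTT |

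**Count.**
- Hematology: 6 items in the protocol, 5 carried over.
- Chemistry: 4 + 2 + 3 = 9 items, all carried over.
- Coagulation: 2 items, both carried over.
- Total: 6 + 9 + 2 = 17 items in the protocol; 5 + 9 + 2 = 16 in the SAP list. The one missing is platelets.

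**Is the gap filled elsewhere in the SAP?** Platelets are not mentioned in the study variables (4.2.2), the table and listing titles (section 11) or the table shells (section 13). The titles of Tables 3.3.1.1 and 3.3.2.1 name no parameters, so their content is set by the list in 9.6.4.

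**Where would platelet values still appear?**
- In listings. SAP 9.1 lists all CRF data, and section 11 has hematology profiles by patient (Listing 2.8.1) and by variable (Listing 4.15.1).
- In the adverse event tables, under a condition. Protocol 8.1.1 counts an abnormal laboratory finding as a possible adverse event, and SAP 9.6.2 tabulates events by treatment. The value must first be reported as an event by the investigator. Under Protocol 8.3.1, full recording ends 10 days after the infusion or at hospital discharge, whichever comes first; later events are recorded only if judged at least possibly related. For a patient discharged after day 10, the discharge platelet count can therefore fall outside full recording.

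Neither route is the shift table that Protocol 9.4.6 describes.

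**The case against.** Several points on the other side have weight.

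- **The omission is probably clerical.** Sixteen of 17 items are carried over, SAP 1.2 declares no change, SAP 4.2.2 covers hematology results as a class, and SAP 1.1 says the plan is to be read with the protocol. A programmer might add platelets unprompted. This makes intent unlikely, but the documents do not settle it, and an enumerated list governs what is programmed and validated.
- **Listings are not the only route.** A reader might infer that a platelet difference between arms could be seen only by going through individual listings. The documents do not support that, because an abnormal count reported as an adverse event would be tabulated by arm. Protocol 8.5 also has the data monitoring committee review relevant laboratory results. These routes are partial: the first depends on investigator reporting within a limited window, and the second is trial oversight and does not supply a table in the study report.
- **Little is lost.** The tables are descriptive. This panel is taken at two times only, screening and hospital discharge, and discharge has no fixed day after a 48-hour infusion. A shift between those times is a blunt instrument for an acute effect. The protocol's summaries of toxicology and phase 1 data report no platelet signal, so nothing here suggests that a known problem is being left out. This limits the importance of the point but does not remove the mismatch.

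**Conclusion.** The point holds as a minor inconsistency between protocol and SAP in safety reporting. One of 17 protocol laboratory items lacks the by-arm shift summary that Protocol 9.4.6 promises, and also lacks the abnormality summary that the SAP gives every other laboratory item. It has no bearing on the primary analysis, power or type I error, and no platelet data are lost, since the values remain in the listings.

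The conclusion rests on two assumptions: that the list in SAP 9.6.4 is followed literally, and that platelet results are captured on the CRF, as Protocol 7.1 and 7.6 require for the laboratory tests. It does not extend to a claim that platelet abnormalities would go unseen or that they were left out on purpose.

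**What to change.** Add platelets to the hematology line in SAP 9.6.4, so that they appear in Table 3.3.1.1 (clinically significant results) and Table 3.3.2.1 (shifts). If the omission was intended, state and justify it in SAP 1.2 instead, although the protocol would then still promise a table that is not produced.

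The cost is one word in the SAP and one further parameter in each of two tables already planned. No new data collection is needed. SAP 1.1 has the plan finalised before database lock, so the change can be made while the analysis is still prespecified.
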